5.1.3.4 Management of Increases in QT Interval

Azithromycin should be discontinued in patients who develop any of the following, unless there is a clear alternative cause for the changes:

- Sustained absolute (at least two ECG measurements >30 minutes apart) QTcF that is >500 ms and >60 ms longer than the baseline value
- Sustained absolute QTcF that is >515 ms
- An episode of torsades de pointes or a new ECG finding of clinical concern

- Of note, if there is a new intraventricular conduction block, the increase in QRS complex duration should be subtracted from the QTcF change, because this represents an increase in QTcF unrelated to alterations in repolarization. Also of note, it is not uncommon to record arrhythmias such as non-sustained ventricular tachycardia, supraventricular tachycardia, pauses, or atrial fibrillation in healthy volunteers receiving placebo during periods of extended ECG monitoring. Therefore, it is critical that expert cardiology advice be sought to confirm any ECG changes and to ascertain the likelihood of a drug-induced arrhythmia versus the background occurrence of this arrhythmia. In such a situation, saving all available ECG data is highly suggested.
- Management of patients with sustained QTcF prolongation should include close monitoring, with ECGs repeated at least hourly until two successive ECGs show resolution of the findings, correction of any electrolyte abnormalities, and possible discontinuation of other concomitant medications that are known to prolong the QT interval. Consultation with a cardiologist or electrophysiologist is recommended to help in the management of such patients.

5.2 SAFETY PARAMETERS AND DEFINITIONS

Safety assessments will consist of monitoring and recording adverse events, including serious adverse events and adverse events of special interest, performing protocol-specified safety laboratory assessments, measuring protocol-specified vital signs, and conducting other protocol-specified tests that are deemed critical to the safety evaluation of the study.

Certain types of events require immediate reporting to the Sponsor, as outlined in Section [5.4](#).

5.2.1 Adverse Events

According to the ICH guideline for GCP, an adverse event is any untoward medical occurrence in a clinical investigation patient administered a pharmaceutical product, regardless of causal attribution. An adverse event can, therefore, be any of the following:

- Any unfavorable and unintended sign (including an abnormal laboratory finding), symptom, or disease temporally associated with the use of a medicinal product, whether or not considered related to the medicinal product
- Any new disease or exacerbation of an existing disease (a worsening in the character, frequency, or severity of a known condition) (see Section [5.3.5.9](#) for more information)
- Recurrence of an intermittent medical condition (e.g., headache) not present at baseline
- Any deterioration in a laboratory value or other clinical test (e.g., ECG, X-ray) that is associated with symptoms or leads to a change in study treatment or concomitant treatment or discontinuation from study drug

5.2.2 Serious Adverse Events (Immediately Reportable to the Sponsor)

A serious adverse event is any adverse event that meets any of the following criteria:

- Is fatal (i.e., the adverse event actually causes or leads to death)
- Is life threatening (i.e., the adverse event, in the view of the investigator, places the patient at immediate risk of death)

This does not include any adverse event that, had it occurred in a more severe form or was allowed to continue, might have caused death.

- Requires or prolongs inpatient hospitalization (see Section [5.3.5.10](#))
- Results in persistent or significant disability/incapacity (i.e., the adverse event results in substantial disruption of the patient's ability to conduct normal life functions)
- Is a congenital anomaly/birth defect in a neonate/infant born to a mother exposed to study drug
- Is a significant medical event in the investigator's judgment (e.g., may jeopardize the patient or may require medical/surgical intervention to prevent one of the outcomes listed above)

The terms "severe" and "serious" are not synonymous. Severity refers to the intensity of an adverse event (e.g., rated as mild, moderate, or severe, or according to WHO Toxicity Grading Scale; see Section [5.3.3](#)); the event itself may be of relatively minor medical significance (such as severe headache without any further findings).

Severity and seriousness need to be independently assessed for each adverse event recorded on the eCRF.

Serious adverse events are required to be reported by the investigator to the Sponsor immediately (i.e., no more than 24 hours after learning of the event; see Section [5.4](#) for reporting instructions).

5.2.3 Adverse Events of Special Interest (Immediately Reportable to the Sponsor)

Adverse events of special interest are required to be reported by the investigator to the Sponsor immediately (i.e., no more than 24 hours after learning of the event; see Section [5.4](#) for reporting instructions). Adverse events of special interest for this study are as follows:

- Cases of potential drug-induced liver injury that include an elevated ALT or AST in combination with either an elevated bilirubin or clinical jaundice, as defined by Hy's Law (see Section [5.3.5.6](#))

5.3 METHODS AND TIMING FOR CAPTURING AND ASSESSING SAFETY PARAMETERS

The investigator is responsible for ensuring that all adverse events (see Section 5.1.3 for definition) are recorded on the Adverse Event eCRF and reported to the Sponsor in accordance with instructions provided in this section and in Sections 5.3–5.5. The investigator is also responsible for reporting medical device complaints.

For each adverse event recorded on the Adverse Event eCRF, the investigator will make an assessment of seriousness (see Section 5.2.2 for seriousness criteria), severity (see Section 5.3.3), and causality (see Section 5.3.4).

5.3.1 Adverse Event Reporting Period

Investigators will seek information on adverse events at each patient contact. All adverse events, whether reported by the patient or noted by study personnel, will be recorded in the patient's medical record and on the Adverse Event eCRF.

After informed consent has been obtained but prior to initiation of study randomization, only serious adverse events caused by a protocol-mandated intervention (e.g., invasive procedures such as biopsies, discontinuation of medications) should be reported (see Section 5.3.2 for instructions for reporting serious adverse events).

After randomization, all adverse events will be reported until 28 days after the final dose of azithromycin.

Instructions for reporting adverse events that occur after the adverse event reporting period are provided in Section 5.5.

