2.2 SAFETY OBJECTIVE

The safety objective for this study is to evaluate the safety of ^{129}Xe MRI procedures and of AZM+SOC compared with SOC on the basis of the following endpoints:

- Incidence and severity of adverse events, with severity determined according to the World Health Organization (WHO) toxicity scale
- Change from baseline in targeted vital signs
- Change from baseline in targeted clinical laboratory test results
- Change from baseline in ECG data

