5.3.5.7 Deaths

All deaths that occur during the protocol-specified adverse event reporting period (see Section 5.2.1), regardless of relationship to study drug, must be recorded on the Adverse Event eCRF and immediately reported to the Sponsor (see Section 5.3.2). This includes death attributed to progression of COPD.

Death should be considered an outcome and not a distinct event. The event or condition that caused or contributed to the fatal outcome should be recorded as the single medical concept on the Adverse Event eCRF. Generally, only one such event should be reported. If the cause of death is unknown and cannot be ascertained at the time of reporting, "**unexplained death**" should be recorded on the Adverse Event eCRF. If the cause of death later becomes available (e.g., after autopsy), "unexplained death" should be replaced by the established cause of death. The term "**sudden death**" should not be used unless combined with the presumed cause of death (e.g., "sudden cardiac death").

If the death is attributed solely to progression of COPD, "Chronic Obstructive Pulmonary Disease progression" should be recorded on the Adverse Event eCRF.

Deaths that occur after the adverse event reporting period should be reported as described in Section 5.5.

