5.6 ADVERSE EVENTS THAT OCCUR AFTER THE ADVERSE EVENT REPORTING PERIOD

The Sponsor should be notified if the investigator becomes aware of any serious adverse event that occurs after the end of the adverse event reporting period (defined as 28 days after the final dose of study drug), if the event is believed to be related to prior study treatment. These events should be reported through use of the Adverse Event

¹²⁹Xe MRI—Genentech, Inc.

66/Protocol GE42063, Version 5

eCRF. However, if the EDC system is not available, the investigator should report these events directly to the Sponsor or its designee, either by faxing or by scanning and emailing the paper Clinical Trial Serious Adverse Event/Adverse Event of Special Interest Reporting Form using the fax number or email address provided to investigators.

5.7 EXPEDITED REPORTING TO HEALTH AUTHORITIES, INVESTIGATORS, INSTITUTIONAL REVIEW BOARDS, AND ETHICS COMMITTEES

The Sponsor will promptly evaluate all serious adverse events and adverse events of special interest against cumulative product experience to identify and expeditiously communicate possible new safety findings to investigators, IRBs, ECs, and applicable health authorities based on applicable legislation.

To determine reporting requirements for single adverse event cases, the Sponsor will assess the expectedness of these events through use of the reference safety information in the documents listed below:

Drug	Document
Azithromycin	Single drug covered by prescribing information: Azithromycin E.U. Summary of Product Characteristics
¹²⁹ Xe MRI	Drug device combination covered by combination Investigator's Brochure: HP ¹²⁹ Xe and MRI Investigator's Brochure

HP = hyperpolarized; MRI = magnetic resonance imaging.

The Sponsor will compare the severity of each event and the cumulative event frequency reported for the study with the severity and frequency reported in the applicable reference document.

Reporting requirements will also be based on the investigator's assessment of causality and seriousness, with allowance for upgrading by the Sponsor as needed.

A SMC will monitor the incidence of the above-listed anticipated events during the study. An aggregate report of any clinically relevant imbalances that do not favor the test product will be submitted to health authorities.

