Appendix 1: Schedule of Activities

	Screening	Treatment Period						End of Tx	Safety Follow-Up ^a	ET ^b	UV
		1	2 ^c	3	4	5	6 ^d				
Visit No.		1	2 ^c	3	4	5	6 ^d	7	8 ^e		
Week (Window, days)		0 -28 to -1	(± 4)	6 (± 4)	12 (± 7)	24 (± 7)	36 (± 7)	48 (± 7)	52 (± 7)		
Concomitant medications		x	x	x	x	x	x	x	x	x	x
AEx			x	x	x	x	x	x	x	x	x
Health care utilizations ^{aa}			x	x	x	x	x	x	x	x	x
Adverse events ^{bb}			x	x	x	x	x	x	x	x	x
Study drug Rx (3-month supply) ^{cc}			x		x	x	x				
Patient diary review ^{dd}				x	x	x	x	x			

6MWT = six-minute walking test; AEx = acute exacerbations; BORG CR10 Scale = Borg Category-Ratio 10 Scale[®]; COPD = chronic obstructive pulmonary disease; CT = computed tomography; DL_{CO} = carbon monoxide diffusing capacity; ET = early termination; FEV₁ = forced expiratory volume; HHIE-S = Hearing Handicap Inventory in the Elderly—Screening Questionnaire; HRCT = high-resolution computed tomography; IRB = Institutional Review Board; KCO = carbon monoxide transfer coefficient; mMRC = Modified Medical Research Council; MRI = magnetic resonance imaging; PRO = patient-reported outcome; Rx = prescription; SGRQ-C = St. George's Respiratory Questionnaire—COPD; SNP = single nucleotide polymorphism; SOA = Schedule of Activities; SOC = standard of care; SpO₂ = oxygen saturation; Tx = treatment; UV = unscheduled visit.

^a Safety follow-up will take place via telephone interview for adverse events, health care utilization, and change in medications.

^b The ET visit applies to patients who discontinue study drug prematurely.

^c All baseline assessments at Visit 2 must be completed prior to the first dose of study drug (azithromycin). Azithromycin will only be dispensed to patients randomized to study drug in Cohort A.

^d Patients in Cohort B will be assessed by telephone call from site staff. Assessments limited to changes in concomitant medications, AEx, health care utilizations, and adverse events occurring between Week 24 and Week 36.

^e Limited to patients in Cohort A only.

^f Written informed consent for participation in the study must be obtained before performing any study-specific tests or evaluations.

^g Demographic data will include age (date of birth), sex, and self-reported race/ethnicity.

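### Section 5.3.1 ends adverse event reporting by the last azithromycin dose: no anchor for about 70 of 120 patients, and an early close for azithromycin patients who stop but stay on study

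*Combined protocol and SAP*

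**What the plan says.** Section 5.3.1 gives one close for adverse event (AE) reporting: "After randomization, all adverse events will be reported until 28 days after the final dose of azithromycin". The same section opens with an instruction that carries no time limit: "Investigators will seek information on adverse events at each patient contact". Section 5.3.2 has events elicited at all evaluation timepoints, and Section 4.5.13 has the investigator ask about them since the last visit.

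Section 3.1 gives Cohort A four further weeks of safety evaluation after the treatment period and does not restrict this to the azithromycin arm. Section 4.6.2 ends Cohort A with a telephone safety call at Week 52 and Cohort B at the Week 48 visit. The AE row of Appendix 1 is marked at every visit from Visit 2 to Visit 8, with Visit 8 limited to Cohort A.

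Azithromycin is dispensed only to Cohort A patients randomized to it (Appendix 1, footnote c). Patients who stop it are asked to continue all other assessments to the end of the study (4.5.5, in the hearing section) and return for scheduled visits (4.6.1). Footnote b of Appendix 1 adds: "The ET visit applies to patients who discontinue study drug prematurely".

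Other rules hang on the reporting period or set their own close:

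- Section 5.3.5.7 requires recording, regardless of relationship, of "All deaths that occur during the protocol-specified adverse event reporting period".
- Section 5.6 describes the period as "defined as 28 days after the final dose of study drug". After it, notification is asked only for serious events, and only "if the event is believed to be related to prior study treatment".
- Section 5.4.2.2 ends reporting of serious events and events of special interest 28 days after the last dose of *study treatment*.

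The anchor terms are not used consistently. Footnote c equates *study drug* with azithromycin: "All baseline assessments at Visit 2 must be completed prior to the first dose of study drug (azithromycin". Sections 4.3.1 and 4.3.2 place both azithromycin and HP ¹²⁹Xe under *study treatment*. Section 6.5 requires a dose of *study drug* for the safety population yet reports a SOC group, and it starts treatment-emergent events at the first dose of *study treatment* with no end cut.

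**The concern.** The safety objective in Section 2.2 covers ¹²⁹Xe "MRI procedures and of AZM+SOC compared with SOC on the basis of the following endpoints", the first of which is the incidence and severity of AEs. A fair comparison of incidence needs the same period of observation in both arms. A close tied to the last azithromycin dose can shorten that period only in the azithromycin arm.

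The early close can also follow a side effect. The stopping rules for hearing changes and for *C. difficile* diarrhea in Section 4.6.1 are specified for azithromycin patients. The hearing questionnaire is scheduled after screening at Weeks 12, 24 and 48, so stops at Weeks 12 and 24 are foreseeable.

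The ¹²⁹Xe part of the objective is touched as well, because an early stopper still has scheduled scans after the stated close. The trial is open-label, so a site that follows the written close and a site that follows the schedule could each believe it is compliant while collecting different data.

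**Working it through.** **Inputs.** Maximum 336 once-daily doses (4.3.2.1); close 28 days after the final dose (5.3.1); Cohort A participation of about 52 weeks (3.2); AE contacts at Weeks 0, 6, 12, 24, 36, 48 and 52, which is seven, and scans at Weeks 0, 6, 12, 24 and 48 (Appendix 1); about 100 patients randomized 1:1 in Cohort A and about 20 in Cohort B (3.1).

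**1. The plan's own figure.** 336 / 7 = 48 weeks of dosing. (336 + 28) / 7 = 364 / 7 = 52 weeks. This matches the stated 52 weeks, so the rule works for a patient who completes azithromycin.

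**2. Patients with no anchor.** 100 / 2 = 50 in the SOC arm, plus 20 in Cohort B, is 70 of 120.

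**3. Azithromycin patients who stop at week t and stay on study.** Close = t + 4. Shortfall = 52 − (t + 4) = 48 − t. Nominal visit weeks are used, and any early termination visit is left out.

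| Stop week | Close | Weeks short of 52 | AE contacts after close (of 7) | Scans after close |
|---|---|---|---|---|
| 6 | 10 | 42 | 5 (Weeks 12, 24, 36, 48, 52) | Weeks 12, 24, 48 |
| 12 | 16 | 36 | 4 (Weeks 24, 36, 48, 52) | Weeks 24, 48 |
| 24 | 28 | 24 | 3 (Weeks 36, 48, 52) | Week 48 |
| 36 | 40 | 12 | 2 (Weeks 48, 52) | Week 48 |

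**4. Arm-level illustration.** The documents give no azithromycin stopping rate. Assume that a share q of the arm stops, at times spread evenly over 48 weeks, and that all are followed to Week 52. The mean shortfall per stopper is then 24 weeks and the arm's mean window is 52 − 24q. For q = 5%, 10%, 20% and 30% this is 50.8, 49.6, 47.2 and 44.8 weeks, or 2.3%, 4.6%, 9.2% and 13.8% shorter than 52. This measures reporting time, not events lost.

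**5. Serious events, under two readings of *study treatment* in 5.4.2.2.**

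- Azithromycin only: the close is t + 4, as in 5.3.1, and SOC and Cohort B again have no anchor.
- Azithromycin or HP ¹²⁹Xe: a patient scanned at Week 48 closes at 48 + 4 = Week 52, whatever the azithromycin stop date. Cohort B would also run to Week 52, although its last contact is Week 48.

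The documents do not settle which reading applies.

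**The case against.** The strongest reply is that the plan already says when AE collection ends, in every place except one sentence. Sections 3.1, 4.5.13, 4.6.2 and 5.3.2, the opening of 5.3.1 and the Appendix 1 AE row together carry collection to Week 52 in Cohort A and Week 48 in Cohort B. Section 6.5 applies no end cut to treatment-emergent events, so a late event that is recorded is also analysed. Exacerbations have their own eCRF (4.5.13), so the primary endpoint does not depend on 5.3.1. All of this stands. What remains is that none of these passages defines the reporting period, while 5.3.5.7 and 5.6 rely on one, and the only explicit close contradicts the schedule for early stoppers.

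A reader might infer more than the documents support:

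- *AEs are not collected in the 70 patients without azithromycin.* They are scheduled; only 5.3.1 lacks an end date for them.
- *The comparison is biased in favour of azithromycin.* A shorter period lowers recorded events in that arm, but Appendix 1 footnote bb gives azithromycin patients additional hearing questions, which pushes the other way. The net direction is not known.
- *Serious events and deaths after the close go unreported.* That depends on reading the anchor terms as azithromycin only, and usage is mixed.
- *The SOC safety group is empty.* Taken literally with footnote c, 6.5 would say so, but it names a SOC group and the intent is plain. No separate SAP definition of the safety set was in the text reviewed, so this part is held with less confidence.

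**Conclusion.** The inconsistency in Section 5.3.1 is established and should be corrected. The stated close suits only azithromycin completers. The 12 to 42 week shortfall at the four stop weeks examined is exact for nominal visits and assumes that the patient stays on study to Week 52.

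The consequence is conditional. If sites apply the written close, non-serious AE recording is shorter in one arm of a planned safety comparison. If they follow the schedule, events are captured. The risk is therefore uneven reporting between arms and sites, not demonstrated loss, and the number of events at stake cannot be derived. Any effect on serious events and deaths remains open until the anchor terms are defined.

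**What to change.** - In 5.3.1, state that all AEs are reported from randomization or enrolment to the patient's final scheduled study contact (Week 52 in Cohort A, Week 48 in Cohort B), regardless of azithromycin status.
- Use one defined term, saying whether it includes HP ¹²⁹Xe, in 5.3.1, 5.3.5.7, 5.4.2.2, 5.6 and 6.5, and in the SAP if it uses the same words.
- Word 6.5 so that SOC patients belong to the safety population without an azithromycin dose. Requiring azithromycin or ¹²⁹Xe instead would drop a randomized SOC patient who was never scanned.
- Reconcile footnote b on the early termination visit with 4.5.5 and 4.6.1, which keep such patients on scheduled visits.
- Correct the cross-references: 5.3.1 and 5.3.5.7 send events and deaths after the period to 5.5, but the rule is in 5.6; 5.3.5.7 cites 5.2.1 for a period set in 5.3.1.

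The cost is protocol wording and any matching SAP wording. Appendix 1 already has the contacts, so no visit or call is added. The downside is a few more AE entries for patients who stopped azithromycin.

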5.3.2 Eliciting Adverse Event Information

A consistent methodology of non-directive questioning should be adopted for eliciting adverse event information at all patient evaluation timepoints. Examples of non-directive questions include the following:

"How have you felt since your last clinic visit?"

"Have you had any new or changed health problems since you were last here?"

5.3.3 Assessment of Severity of Adverse Events

The WHO toxicity grading scale (see Appendix 5) will be used for assessing adverse event severity. Table 2 will be used for assessing severity for adverse events that are not specifically listed in the WHO toxicity grading scale.

Table 2 Adverse Event Severity Grading Scale for Events Not Specifically Listed in WHO Toxicity Grading Scale

Grade	Severity
1	Mild; transient or mild discomfort (<48 hours); no medical intervention or therapy required
2	Moderate; mild to moderate limitation in activity; some assistance may be needed; no or minimal medical intervention or therapy required
3	Severe; marked limitation in activity; some assistance usually required; medical intervention or therapy required; hospitalization possible
4	Life-threatening; extreme limitation in activity; significant assistance required; significant medical intervention or therapy required, hospitalization or hospice care probable

WHO=World Health Organization.

Notes: Developed by the Division of Microbiology and Infectious Diseases.

Regardless of severity, some events may also meet seriousness criteria. Refer to definition of a serious adverse event (see Section [5.2.2](#)).

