4.6 TREATMENT, PATIENT, STUDY, AND SITE DISCONTINUATION

4.6.1 Study Treatment Discontinuation

Patients must permanently discontinue study treatment if they experience any of the following:

- Any medical condition that the investigator or Sponsor determines may jeopardize the patient's safety if he or she continues to receive study treatment

- Investigator or Sponsor determination that treatment discontinuation is in the best interest of the patient
- Any Grade 4 adverse event that the investigator determines to be related to study treatment

This excludes COPD exacerbations, unless they meet one of the other criteria for study treatment discontinuation.
- Pregnancy
- Development of *C. difficile* diarrhea (*for patients in Cohort A randomized to azithromycin*)
- *Any onset hearing loss, worsening hearing loss, hearing disturbance, or decline in the interpretation of the HHIE-S score (for patients in Cohort A randomized to azithromycin)*

The primary reason for study treatment discontinuation should be documented on the appropriate eCRF. Patients who discontinue study treatment will not be replaced.

Patients will return to the clinic for scheduled study visits after the final dose of study drug (see [Appendix 1](#) for additional details).

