5.1.3.2 Treatment Interruption

Study treatment may be temporarily suspended in patients who experience toxicity considered to be related to study drug. If study treatment has been withheld for two or more consecutive dosing visits because of toxicity, the patient should be discontinued from study treatment. However, if the adverse event(s) that led to withholding dosing shows clear evidence of improvement in the investigator's judgment, treatment may be resumed; the Medical Monitor may be consulted as appropriate.

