SpO_2 should not be monitored during the 6MWT procedure. Patients should immediately stop the 6MWT procedure if any of the following occur:

- Chest pain
- Light headedness
- Intolerable dyspnea
- Leg cramps
- Staggering
- Diaphoresis
- Pale or ashen appearance
- Mental confusion or headache

Appendix 5

WHO Toxicity Grading Scale

ITEM	Grade 1 Toxicity	Grade 2 Toxicity	Grade 3 Toxicity	Grade 4 Toxicity
HEMATOLOGY				
Hemoglobin	9.5–10.5 g/dL	8.0–9.4 g/dL	6.5–7.9 g/dL	< 6.5 g/dL
Absolute neutrophil count	1000–1500/mm ³	750–999/mm ³	500–749/mm ³	<500/mm ³
Platelets	75,000–99,000/mm ³	50,000–74,999/mm ³	20,000–49,000/mm ³	<20,000/mm ³
PT	1.01–1.25 × ULN	1.26–1.5 × ULN	1.51–3.0 × ULN	>3 × ULN
aPPT	1.01–1.66 × ULN	1.67–2.33 × ULN	2.34–3 × ULN	> 3 × ULN
Fibrinogen	0.75–0.99 × LLN	0.50–0.74 × LLN	0.25–0.49 × LLN	< 0.25 × LLN
Fibrin split product	20–40 µg/mL	41–50 µg/mL	51–60 µg/mL	> 60 µg/mL
Methemoglobin	5%–9.9%	10.0%–14.9%	15.0%–19.9%	> 20%
LIVER ENZYMES				
AST (SGOT)	1.25–2.5 × ULN	2.6–5 × ULN	5.1–10 × ULN	> 10 × ULN
ALT (SGPT)	1.25–2.5 × ULN	2.6–5 × ULN	5.1–10 × ULN	> 10 × ULN
GGT	1.25–2.5 × ULN	2.6–5 × ULN	5.1–10 × ULN	> 10 × ULN
ALP	1.25–2.5 × ULN	2.6–5 × ULN	5.1–10 × ULN	> 10 × ULN
Amylase	1.1–1.5 × ULN	1.6–2.0 × ULN	2.1–5.0 × ULN	> 5.1 × ULN
CHEMISTRIES				
Hyponatremia	130–135 mEq/L	123–129 mEq/L	116–122 mEq/L	< 116 or mental status changes or seizures
Hypernatremia	146–150 mEq/L	151–157 mEq/L	158–165 mEq/L	> 165 mEq/L or mental status changes or seizures
Hypokalemia	3.0–3.4 mEq/L	2.5–2.9 mEq/L	2.0–2.4 mEq/L or intensive replacement Rx required or hospitalization required	< 2.0 mEq/L or paresis or ileus or life-threatening arrhythmia
Hyperkalemia	5.6–6.0 mEq/L	6.1–6.5 mEq/L	6.6–7.0 mEq/L	> 7.0 mEq/L or life-threatening arrhythmia
Hypoglycemia	55–64 mg/dL	40–54 mg/dL	30–39 mg/dL	<30 mg/dL or mental status changes or coma
Hyperglycemia (note if fasting)			251–500 mg/dL	> 500 mg/dL or ketoacidosis or seizures
Hypocalcemia (corrected for albumin)	8.4–7.8 mg/dL	7.7–7.0 mg/dL	6.9–6.1 mg/dL	< 6.1 mg/dL or life-threatening arrhythmia or tetany

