Appendix 5: WHO Toxicity Grading Scale

ITEM	Grade 1 Toxicity	Grade 2 Toxicity	Grade 3 Toxicity	Grade 4 Toxicity
Neuro control	Mild difficulty concentrating; no Rx; mild confusion/agitation; ADL unaffected	Moderate confusion/agitation some limitation of ADL; minimal Rx	Severe confusion/agitation needs assistance for ADL; therapy required	Toxic psychosis; hospitalization
Muscle strength	Subjective weakness; no objective symptoms/signs	Mild objective signs/symptoms; no decrease in function	Objective weakness function limited	Paralysis
OTHER PARAMETERS				
Fever: oral, > 12 hours	37.7°C –38.5°C or 100.0°F –101.5°F	38.6°C –39.5°C or 101.6°F –102.9°F	39.6°C –40.5°C or 103°F –105°F	> 40°C or > 105°F
Headache	Mild, no Rx therapy	Transient, moderate; Rx required	Severe; responds to initial narcotic therapy	Intractable; required repeated narcotic therapy
Fatigue	No decrease in ADL	Normal activity decreased 25%–50%	Normal activity decreased > 50% can't work	Unable to care for self
Allergic reaction	Pruritus without rash	Localized urticaria	Generalized urticaria; angioedema	Anaphylaxis
Local reaction	Tenderness or erythema	Induration < 10 cm or phlebitis or inflammation	Induration > 10 cm or ulceration	Necrosis
Mucocutaneous	Erythema; pruritus	Diffuse, maculopapular rash, dry desquamation	Vesiculation, moist desquamation, or ulceration	Exfoliative dermatitis, mucous membrane involvement or erythema, multiforme or suspected Stevens-Johnson or necrosis requiring surgery

ADL=activities of daily living; FEV₁=forced expiratory volume in 1 second; LLN=lower limit of normal; Rx=treatment; ULN=upper limit of normal.

Appendix 6

Borg Category Ratio 10 Scale®

Instruction. Use this rating scale to report how strong your perception is. It can be exertion, pain or something else. First look at the verbal expressions. Start with them and then the numbers. Of these ten (10) or "Extremely strong", "Maximal" is a very important intensity level. This is the most intense perception or feeling you have ever had.

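### The Appendix 5 fever row gives readings of 40.1 to 40.5°C two grades, and one of them triggers a compulsory stop when the fever is judged related

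*Combined protocol and SAP*

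**What the plan says.** Section 2.2 makes graded severity a safety endpoint: "Incidence and severity of adverse events, with severity determined according to the World Health Organization (WHO) toxicity scale". Section 5.3.3 names the instrument: "The WHO toxicity grading scale (see Appendix 5) will be used for assessing adverse event severity". Table 2 in that section is reserved for events that Appendix 5 does not list. Fever is listed, so Appendix 5 governs it.

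The row is labelled "Fever: oral, > 12 hours". Its Grade 3 cell is "39.6°C –40.5°C or 103°F –105°F". Its Grade 4 cell gives two limits joined by an or: above 40°C, or above 105°F.

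Section 4.6.1 attaches a consequence to the top grade. Among the events that make permanent discontinuation of study treatment compulsory is "Any Grade 4 adverse event that the investigator determines to be related to study treatment".

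**The concern.** A grading row should give one grade to one measurement. Here the Grade 3 Celsius range runs past the point where Grade 4 starts, and the Fahrenheit limits draw the line somewhere else. Two investigators who both follow the table can grade the same unexplained fever differently. If they judge it related, one must stop treatment permanently and the other need not. The safety summaries by grade inherit the same inconsistency.

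The choice of unit may also matter. Cohort A is stratified by United States against United Kingdom/Canada, and the vital signs section (4.5.4) names no temperature unit. If sites record in different units, which is an assumption, the grade could depend on the site's thermometer scale.

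**Working it through.** The plan has no power or sample-size figure on this point. The check compares the printed limits.

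**Inputs (Appendix 5, fever row).** Grade 3: 39.6 to 40.5°C, or 103 to 105°F. Grade 4: above 40°C, or above 105°F.

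**Do the paired limits agree?** Use °F = °C × 9/5 + 32.
- Grade 3 upper limit: 40.5 × 9/5 + 32 = 104.9°F, against a printed 105°F. They agree to 0.1°F.
- Grade 4 limit: 40 × 9/5 + 32 = 104.0°F, against a printed 105°F. They differ by 1.0°F.
- In the other direction, (105 − 32) × 5/9 = 40.56°C, so the two halves of the Grade 4 cell are 0.56°C apart.

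Three of the four limits sit at about 40.5°C/105°F. The 40°C limit is the odd one out.

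**Which grades does each reading meet?**

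| °C | °F | Celsius limits met | Fahrenheit limits met |
|---|---|---|---|
| 40.0 | 104.0 | 3 | 3 |
| 40.1 | 104.2 | 3 and 4 | 3 |
| 40.2 | 104.4 | 3 and 4 | 3 |
| 40.3 | 104.5 | 3 and 4 | 3 |
| 40.4 | 104.7 | 3 and 4 | 3 |
| 40.5 | 104.9 | 3 and 4 | 3 |
| 40.6 | 105.1 | 4 | 4 |

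At 0.1°C steps, the Grade 3 range 39.6 to 40.5°C holds 10 readings, and 5 of them are also Grade 4.

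**Is this how the table normally works?** Thirty rows have numeric limits in both Grade 3 and Grade 4: hematology 8, liver enzymes and amylase 5, chemistries 13, and one each for proteinuria, hemorrhage, bronchospasm and fever (8 + 5 + 13 + 4 = 30). Fever is the only one whose Grade 3 range runs past the Grade 4 limit in the same unit. Hyperkalemia shows the usual pattern: Grade 3 ends at 7.0 mEq/L and Grade 4 is anything above that.

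**Does other text settle it?** Section 5.3.5.3 deals with a persistent event that becomes more severe. The highest-grade rule in Section 6.5 deals with events whose severity varies, and only for the summaries. Both lean toward the higher grade. Neither assigns a grade to a single reading that fits two.

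**After the change.** With Grade 4 above 40.5°C, 0 of the 10 Celsius Grade 3 readings carry two grades. The Celsius and Fahrenheit Grade 4 limits then differ by 40.56 − 40.5 = 0.06°C, which is conversion rounding.

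**The case against.** The best reply is that the table only works if the highest grade met is assigned. The Grade 4 cell is an either/or, so 40.3°C satisfies it. Other rows also let a patient meet two grades through different criteria: a potassium of 2.0 to 2.4 mEq/L (Grade 3) with paresis (Grade 4), or more than 7 loose stools a day (Grade 3) with hospitalization for IV fluids (Grade 4). This stands in part. A reader might infer that fever is the only row where two grades can apply, and that would be wrong. The fever row is distinctive because a single measurement in a single unit meets both grades. The protocol states no highest-grade rule for that case, and such a rule would contradict the row's own Fahrenheit cell.

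The second reply is that the consequence is remote, and most of this stands. The fever must be oral, last more than 12 hours, peak in a half-degree band and be judged related. A known diagnosis is recorded in place of the sign (5.3.5.1), and fever explained by intercurrent illness counts as unrelated (Table 3). A reader might infer that a patient could be kept on treatment unsafely because of this cell. The documents do not support that. Section 4.6.1 also compels a stop on "Investigator or Sponsor determination that treatment discontinuation is in the best interest of the patient", and Section 5.1.3.2 adds: "Study treatment may be temporarily suspended in patients who experience toxicity considered to be related to study drug".

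A reader might also try to count those affected from the roughly 50 patients randomized to azithromycin. That denominator is not secure. Section 4.3 lists hyperpolarized xenon as an investigational product, and Section 4.3.1 describes it under study treatment. The Grade 4 criterion, unlike the *C. difficile* and hearing criteria in the same list, is not limited to azithromycin.

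**Conclusion.** The fever row is wrong as written, and the point is minor. Readings of 40.1 to 40.5°C have two grades in Celsius and one in Fahrenheit, and the Grade 4 limits are 0.56°C apart. The finding rests on the printed limits and unit conversion alone.

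The number of patients affected cannot be stated, because the documents give no rate of related fever in this band. The conditions that must coincide suggest very few. A stronger reading, that the error bears on the primary endpoint or on power, has no support: fever grade enters neither. A patient who stops azithromycin is asked to continue the other assessments (4.5.5).

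That about 40.5°C was the intended limit is an inference from the other three limits in the row. The documents do not say so.

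**What to change.** In the fever row of Appendix 5, change the Grade 4 Celsius limit from above 40°C to above 40.5°C. This matches the Grade 3 upper limit and agrees with 105°F to within rounding. It is one limit in one cell and needs no new data.

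There are two costs. It is the less cautious limit, since 40.1 to 40.5°C leaves the compulsory Grade 4 stop, although treatment can still be stopped or suspended on judgment. It also edits a scale that Section 2.2 names as the endpoint's instrument, so the change should be declared in the amendment.

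Do not add a sentence to Section 5.3.3 requiring conversion to Celsius and rounding to 0.1°C. It would contradict the printed Fahrenheit cells at seven readings (99.8, 99.9, 101.4, 101.5, 103.0, 103.1 and 105.0°F). For example, 105.0°F is printed as Grade 3 but would round to 40.6°C, which is Grade 4.

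If the sponsor prefers the cautious reading, a sentence in Section 5.3.3 assigning the higher grade whenever a reading meets two also resolves the overlap and leaves the scale unedited. Its weakness is that a site reading only the Fahrenheit limits would still assign Grade 3 at 104.2 to 104.9°F.
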